8.2.5 Re-treatment Criteria

In order to proceed to the next cycle, subjects must continue to meet entry criteria regarding renal and hepatic function (see Section 7.3). Thus, subjects will have laboratory assessments performed to evaluate organ function prior to starting each cycle (including Cycle 1). Because of the time it takes to obtain results from the central laboratory, samples should be collected early enough prior to starting the next cycle in order to allow sufficient time for review. In the event that immediate laboratory assessment is needed, local laboratory measurement is acceptable for starting the next cycle pending the outcome of the central laboratory assessment (ie, in addition to collecting the local laboratory sample, a second sample should be collected and sent to the central laboratory).

The start of the next cycle will be delayed if the subject does not meet entry criteria regarding renal and hepatic function. If there is a delay of more than 42 days (6 weeks) in the start of the next cycle, the Medical Monitor must be consulted. Study treatment should be discontinued if there is a delay of more than 56 days (8 weeks) in the start of the next cycle, unless, in the opinion of the investigator and the Medical Monitor, the subject is experiencing clinical benefit. Justification of the subject continuing in the study must be recorded in the source documents.

[figure not shown]
For subjects that experience hematotoxicity (ANC or platelet drop to Grade 4, or 50% drop within Grade 4) hematologic recovery is required before starting the next cycle at Day 28. When this occurs later than Cycle 6, contact the Celgene Medical Monitor to discuss if the re-treatment criteria are met.

Hematologic recovery defined as:

ANC or platelets Day 1 \geq ANC or platelets nadir from previous Cycle + (0.5 x [ANC or platelets Day 1 – ANC or platelets nadir from previous Cycle])

Note: Following dose adjustments, cycle duration should return to 28 days.

Figure 2: Decision Tree for Hematologic Recovery

ANC=Absolute Neutrophil Count; IP=Investigational Product.

When the dose level is adjusted, weekly hematology monitoring is required for 2 cycles including the cycle in which the adjusted dose or dosing schedule was applied as well as the following cycle. During those 2 cycles, the following dose modification rule, based on ANC or platelets, is applied:

- Subjects that experience a drop in the ANC or platelets during a cycle (drop to Grade 4 or for > 50% drop for subject with Grade 4 at Day 15 or Day 8) will hold the dose for the remaining cycle.

- If dose was held, the start of next cycle is based on ANC or platelet recovery, see flow chart in [Section 8.2.5](#) Re-Treatment Criteria.

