Subjects who have their IP dose reduced or treatment schedule modified may return to their original dose and/or schedule in a step-wise fashion upon discussion and agreement between the investigator and the Medical Monitor provided that the increased dose or treatment schedule is tolerable and at least two additional treatment cycles have occurred since the dose reduction or treatment schedule modification. The treatment schedule should first be increased from 7 to 14 days and then 14 to 21 days, followed by a dose escalation step from 200 to 300 mg.

The dose/treatment schedule modifications steps for 21 days schedule are:

	Dose/schedule		
	300 mg/21d		Level 1
Dose escalation step	200 mg/21d	Dose reduction step	Level -1
Dose escalation step	200 mg/14d	Dose reduction step	Level -2
Dose escalation step	200 mg/7d	Dose reduction step	Level -3

Refer to [Section 8.2.5](#) if, despite the temporary interruption, delay or modification of study treatment, the toxicity persists for more than 42 days and is considered by the investigator to be at least possibly related to study treatment.

Following any modification of study treatment or if a dose is missed, the subject should stay on the visit schedule as specified in [Table 1](#). Unscheduled visits may occur to monitor the subject’s toxicities if necessary.

Dose Modification for Febrile Neutropenia

Any subject who experiences febrile neutropenia \geq Grade 3 will have IP held until fever has resolved; must be afebrile for 3 days before re-starting IP, see [Table 2](#). Administration of antibiotic, antiviral and antifungal therapy is strongly recommended.

Dose Modification for Neutropenia Grade 4

- Grade 4 ANC at Day 1 of a cycle:

Subjects with Grade 4 ANC at Day 1 of a cycle are going to be dosed for a maximum of 14 days on the respective dose level 300 mg or 200 mg or a maximum of 7 days when already on a 14-day dosing schedule. If a subject is stable or improving over several cycles, a discussion with the Medical Monitor is necessary to determine the dose schedule, see [Table 2](#).

- ANC change during a cycle:

Subjects who experience a drop in the ANC during a cycle (e.g. from Grade 3 to Grade 4 or for $> 50\%$ drop for subject with Grade 4 at Day 15 or Day 8 [Day 8 during the 1st two cycles]) will hold the dose for the remaining cycle. If subject is stable or improving for several cycles, a discussion with the Medical Monitor is necessary to determine the dose schedule, see [Table 2](#).

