
Neutropenia Grade 4 (related or unrelated to IP)
	
Pre-existing Neutropenia Grade 4
 
 • Subjects with G4 ANC at D1 of a cycle are going to be dosed for a maximum of 14 days on the respective dose level 300 mg or 200 mg or a maximum of 7 days when already on a 14-day dosing schedule. 
If subjects are stable or improving for several cycles, a discussion with the Medical Monitor is necessary to determine the dose schedule.
 
 • If dose was held, the start of next cycle is based on ANC recovery, see flow chart in Section 8.2.5 Re-Treatment Criteria • If the subject continues to experience neutropenia Grade 4 during 2 consecutive cycles, the treatment schedule may be reduced one step. Secondary prophylaxis with G-CSF is strongly recommended. 
Subjects experiencing worsening of Neutropenia to Grade 4 under IP treatment
 
 • Subjects that experience a drop in the ANC during a cycle (e.g., from G3 to G4 or for > 50% drop for subject with G4 at Day 15 or Day 8 [Day 8 during the 1st two cycles]) will hold the dose for the remaining cycle. 
If subject is stable or improving for several cycles, a discussion with the Medical Monitor is necessary to determine the dose schedule.
 
 • If dose was held, the start of next cycle is based on ANC recovery, see flow chart in Section 8.2.5 Re-Treatment Criteria.
	
 • If the subject continues to experience neutropenia Grade 4 during 2 consecutive cycles, the treatment may be reduced one step. Secondary prophylaxis with G-CSF is strongly recommended.

Table 2: Guidelines for Dose Modifications

NCI CTCAE Toxicity Grade	Action
Diarrhea (≥ Grade 3)	
 • Interrupt IP and provide adequate/maximum medical intervention • Resume IP at same dose when toxicity resolves to ≤ Grade 1 • If event reoccurs upon re-challenge or during next treatment cycle, reduce IP dose to 200 mg. • If event reoccurs at same intensity once IP dose is reduced to 200 mg, follow the steps above and modify the treatment schedule at a dose of 200 mg once a day.

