9.1 Permitted Concomitant Medications and Procedures

Best supportive care may be used in combination with study therapy if deemed necessary. Best supportive care in both treatment arms for this study includes, but is not limited to, treatment with RBC or whole blood transfusions, fresh frozen plasma transfusions, single donor or pooled donor platelet transfusions, antibiotic, antiviral and/or antifungal therapy, nutritional support as needed, and granulocyte colony stimulating factors for subjects experiencing neutropenic fever/infections. The use of granulocyte colony stimulating factors is also allowed for secondary prophylaxis under certain conditions as described further below. The use of these products will be considered as concomitant treatment and documented as concomitant medications, therapies or procedures. Additional details on the permitted treatments are detailed below.

Subjects who are currently using iron-chelating agents should be on a stable or decreasing dose for at least 8 weeks (56 days) prior to randomization.

Blood product support (RBCs and platelets) may be administered according to institutional standards. Consider platelet transfusion if platelet counts are $< 25 \times 10^9/L$. If appropriate administration of platelets does not correct the platelet counts, contact the Medical Monitors to consider IP dosing delay. The use of these products will be considered as concomitant treatment, and should be collected on the appropriate CRF.

Subjects may be administered supportive and palliative care (eg, pain control) as clinically indicated throughout the study.

Nausea and vomiting are commonly reported adverse reactions associated with azacitidine treatment and subjects may be pre-medicated for nausea and vomiting prior to IP administration at the investigator's discretion. Serotonin (5-HT₃) receptor antagonists (eg, ondansetron) or other antiemetics may be administered approximately 30 minutes prior to IP administration. Additional doses of serotonin (5-HT₃) receptor antagonists or other antiemetics may be administered if required. Pre-treatment or post-treatment with antiemetic medication will be considered as concomitant treatment and should be recorded on the appropriate CRF.

Treatment with antidiarrheal medications is recommended at the first sign of diarrhea as per the guidelines in [Appendix H](#). Pre-medication with antidiarrheal medication for subsequent doses of

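### The protocol's platelet-toxicity instructions in Sections 8.2.4/Table 2, 8.2.5 and 9.1 do not agree and need to be reconciled

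*Protocol*

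**What the plan says.** Section 8.2.4 has a Grade 4 neutropenia rule for counts that fall during treatment. It opens "Subjects who experience a drop in the ANC during a cycle", holds dosing for the rest of that cycle, and ties the next cycle to ANC recovery. Table 2 repeats it ("Subjects that experience a drop in the ANC during a cycle"). Neither names platelets. Table 2 has no thrombocytopenia row. It does have a general row for hematologic or non-hematologic events of Grade 2 or higher that the investigator judges an unacceptable risk: dosing is interrupted and resumed at Grade 1 or lower.

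Section 8.2.5 covers both cell lines. After an ("ANC or platelet drop to Grade 4, or 50% drop within Grade 4) hematologic recovery is required before starting the next cycle"). Beyond Cycle 6 it adds: "When this occurs later than Cycle 6, contact the Celgene Medical Monitor to discuss if the re-treatment criteria are met". It also contains a within-cycle hold ("Subjects that experience a drop in the ANC or platelets during a cycle"), introduced by: "During those 2 cycles, the following dose modification rule, based on ANC or platelets, is applied". The two cycles are the one in which the dose or schedule was adjusted and the one after it.

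Section 9.1, on supportive care, suggests considering platelet transfusion below 25 x 10^9/L and continues: "If appropriate administration of platelets does not correct the platelet counts, contact the Medical Monitors to consider IP dosing delay".

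Two other places lean on Section 8.2.4. Section 1.4.1 names dose adjustment under it as part of the mitigation for a group of risks that includes thrombocytopenia. Appendix J sends hematologic toxicity in the Extension Phase to it.

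**The concern.** Every subject entered with a platelet count at or below 75 x 10^9/L, and thrombocytopenia is a listed risk of the drug. A severe platelet fall is therefore a foreseeable event, and the protocol should give one clear instruction for it. As written, the answer can depend on which section the site opens. Section 8.2.4 gives an investigator-judged interruption. Section 8.2.5 gives a required recovery before the next cycle. Section 9.1 gives a conversation about a possible delay.

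There are two further gaps. Section 9.1 prompts transfusion, and Section 8.2.5 does not say whether a count raised by transfusion may show recovery. The recovery formula also does not define its terms well enough to be applied in one way. At stake are the safety of subjects still receiving drug and the interpretation of exposure, cycle length and dose-adjustment data.

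**Working it through.** The plan gives no figure to reproduce here. The check is a comparison of the passages, plus algebra on the one formula.

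**Step 1. Trigger, consequence and scope**

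| Place | Trigger for platelets | Consequence | Scope |
|---|---|---|---|
| 8.2.4 and Table 2, Grade 4 rule | None; ANC only | Hold for rest of cycle; restart on ANC recovery | Any cycle |
| 8.2.4 and Table 2, general row | Grade 2 or higher, worse than baseline, unacceptable risk in the investigator's opinion | Interrupt; resume at Grade 1 or lower | Any cycle; discretionary |
| 8.2.5, next cycle | Drop to Grade 4, or 50% drop within Grade 4 | Recovery required | Medical Monitor discussion after Cycle 6 |
| 8.2.5, within cycle | Drop to Grade 4, or more than 50% drop within Grade 4, at Day 8 or 15 | Hold for rest of cycle; restart on ANC or platelet recovery | Only the two cycles tied to a dose adjustment |
| 9.1 | Count not corrected by platelet transfusion (transfusion considered below 25 x 10^9/L) | Contact Medical Monitors; consider a delay | Within or between cycles not stated |

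Two differences follow. Outside the two post-adjustment cycles, an ANC fall to Grade 4 during a cycle has a specific hold and the same platelet fall does not. And there are three standards for resuming: Grade 1 or lower, the formula in 8.2.5, or a discretionary decision with the Medical Monitors.

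**Step 2. The recovery formula**

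Let D be the Day 1 count and N the nadir of the previous cycle. The right-hand side reads "nadir from previous Cycle + (0.5 x [ANC or platelets Day 1" and then subtracts the same nadir. As written:

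- D >= N + 0.5 x (D - N)
- D >= 0.5 x D + 0.5 x N
- 0.5 x D >= 0.5 x N, so D >= N

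Evaluated on all integer pairs from 0 to 100 (101 x 101 = 10,201), the rule agreed with D >= N every time. Read literally, recovery requires no rise above the nadir.

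Suppose instead that the right-hand Day 1 means Day 1 of the previous cycle, B. This is an assumption; the text does not say so. The threshold is then N + 0.5 x (B - N), the midpoint of B and N:

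| B | N | Threshold as written | Threshold if B is meant |
|---|---|---|---|
| 60 | 20 | 20 | 20 + 0.5 x 40 = 40 |
| 40 | 10 | 10 | 10 + 0.5 x 30 = 25 |
| 20 | 9 | 9 | 9 + 0.5 x 11 = 14.5 |

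The values are illustrative. They show that the two readings can give opposite answers for the same subject.

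**Step 3. Transfused counts**

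Other parts of the documents deal with transfusion explicitly. Protocol Appendix D requires pre-treatment counts free of platelet transfusion for 1 week. SAP Appendix F treats platelet values within 7 days after a platelet transfusion as invalid for response. Inclusion criterion 4 makes separate provision for counts within 7 days of a transfusion. Section 8.2.5 has no equivalent statement.

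**The case against.** The strongest defense is that these passages do different jobs and can be obeyed together. Section 9.1 is supportive-care advice prompted by an absolute count. Section 8.2.5 is prompted by a drop and governs the start of the next cycle. A site can support the subject and call the Medical Monitors under one, and still require recovery under the other. Section 8.2.4 refers the reader to 8.2.5, and Appendix J says that Extension Phase dose and schedule follow Section 8.2, which contains 8.2.5. ANC and platelets may also deliberately have different rules.

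Much of this stands, and it rules out several stronger readings that a reader might infer:

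- That 8.2.4 has no rule at all for platelets. The general row covers them at the investigator's discretion, and 8.2.4 allows dosing to be interrupted, delayed or modified for toxicity. What is missing is a platelet-specific rule.
- That one event has three prescribed consequences. The triggers differ, and the documents give no numeric Grade 4 limit for platelets, so equating Grade 4 with the 25 x 10^9/L in Section 9.1 is an assumption. That section also says only to consider transfusion.
- That recovery under 8.2.5 is strictly mandatory. It goes to Medical Monitor discussion after Cycle 6, and the formula as written asks for little.
- That sites did re-dose differently. The documents contain no site-level dosing data.
- That the platelet or bleeding endpoints are at risk from this wording now. Those were due for analysis once, with the primary endpoint, and that report is final with a January 2019 cut-off. The derived platelet response already excludes values soon after transfusion.

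The defense does not cover the restart wording, which is ANC-only in 8.2.4 and Table 2 but ANC or platelets in 8.2.5. Nor does it supply a usable formula or an answer on transfused counts. Cross-references between sections that say different things do not settle which applies. If the two cell lines are meant to differ, the text should say so.

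**Conclusion.** The point holds as a misalignment of instructions. Sections 8.2.4/Table 2, 8.2.5 and 9.1 do not give a site one coherent answer on platelet toxicity, the formula does not state a workable criterion, and the role of transfused counts is open. Different handling of the same fall is a plausible consequence, not a demonstrated one.

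Its frequency cannot be sized from the documents. Assuming a baseline platelet distribution would not help: it would give the share of subjects starting below a given count, not how often the rules conflict.

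Two limits apply. Figure 2, the recovery decision tree, could not be seen and may address platelets; it would not remove the differences in the text around it. Enrollment is closed and the primary analysis is reported, so the practical reach is subjects still on drug, to whom Amendment 6.0 applies, and the reading of exposure data. Nothing here says which clinical rule is right.

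**What to change.** Issue a clarification letter or amendment that reconciles Section 8.2.4, Table 2, Section 8.2.5 (text, formula and Figure 2) and Section 9.1, so that together they state:

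- when a platelet fall triggers a within-cycle hold, and whether this extends beyond the two post-adjustment cycles;
- whether recovery before the next cycle is required or discretionary, and how the general Grade 2 row and Section 9.1 relate to that;
- which Day 1 each term of the recovery formula refers to;
- whether a count taken after platelet transfusion may be used to show recovery.

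Check that the references to Section 8.2.4 in Section 1.4.1 and Appendix J still lead to the agreed instruction. The clinical team decides the content of each item. The cost is protocol wording and its distribution to sites; no sample size, analysis or data-collection change is involved.

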- If dose was held, the start of next cycle is based on ANC recovery, see flow chart in [Section 8.2.5 Re-Treatment Criteria](#), and see dosing table above.

Dose Modification for Diarrhea

It is recommended that subjects experiencing diarrhea be managed according to the guidelines provided in [Appendix H](#). Anti-diarrhea medication may be administered as prophylaxis against diarrhea and for treatment of any adverse events of diarrhea. Dose modifications for diarrhea (\geq Grade 3) are summarized in [Table 2](#).

Dose Modification for Nausea and Vomiting

A serotonin (5-HT₃) receptor antagonist (eg, ondansetron) (or other comparable medication) may be administered as an antiemetic approximately 30 minutes prior to IP administration at the investigator's discretion. Antiemetic medication(s) may be administered for treatment of any adverse events of nausea and/or vomiting. Dose modifications for nausea and vomiting (\geq Grade 3) are summarized in [Table 2](#).

Dose Modification for Renal Dysfunction and Abnormal Serum Electrolytes

If unexplained elevations of serum creatinine or electrolyte disturbances occur, dose or schedule modifications may be implemented as summarized in [Table 2](#).

Dose Modification for Weight Change

No dose adjustment should be made for weight loss or gain alone; however, the reason for weight loss (eg, significant nausea, vomiting, anorexia, etc.) or weight gain (eg, peripheral edema) should be investigated and may require a dose modification as specified in [Table 2](#).

Dose Modification for Other Treatment-Related Non-hematologic Toxicity

Any subject who experiences a treatment-related non-hematologic toxicity \geq Grade 3, that is an escalation from baseline status (see [Section 10.4](#) for baseline definition), may have IP dosing temporarily interrupted until the toxicity returns to \leq Grade 2. Dose modifications for \geq Grade 3 non-hematologic toxicity are summarized in [Table 2](#).

Dose modification for hematologic or non-hematologic adverse events that would put a subject at unacceptable risk in the investigator's opinion (independent of IP relationship)

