Any subject who experiences any hematologic or non-hematologic adverse event \geq Grade 2, that is an escalation from baseline status (see [Section 10.4](#) for baseline definition) and would put a subject at unacceptable risk in the investigator's opinion, may have IP dosing temporarily interrupted until the adverse event returns to \leq Grade 1. Dose modifications for \geq Grade 2 hematologic or non-hematologic adverse events, that would put a subject at unacceptable risk in the investigator's opinion (independent of IP relationship), are summarized in [Table 2](#).

Table 2: Guidelines for Dose Modifications

NCI CTCAE Toxicity Grade	Action

Febrile Neutropenia (≥ Grade 3)
	
 • Hold IP until fever has resolved. • Antibiotic, antiviral and antifungal therapy is strongly recommended. • Resume IP at next lower dose level (see dosing table above) after the fever has resolved and ANC recovery. Contact Medical Monitor. Must be afebrile for 3 days before re-starting IP. • Secondary prophylaxis with G-CSF is strongly recommended.

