Nausea and/or Vomiting (≥ Grade 3)	
 • Interrupt IP and provide adequate/maximal medical intervention • Resume IP at same dose when toxicity resolves to ≤ Grade 1 • If event reoccurs upon re-challenge or at same intensity during next treatment cycle, reduce dose to 200 mg • If event reoccurs at same intensity once IP dose is reduced to 200 mg, follow the steps above and modify the treatment schedule at a dose of 200 mg once a day.
Renal Dysfunction	
 • For unexplained elevations of serum creatinine, delay the start of the next cycle of treatment until values return to baseline. Reduce IP dose in the next cycle of treatment to 200 mg. • The treatment schedule at a dose of 200 mg once a day can be modified if the elevation of serum creatinine recurs in the subsequent cycle. • Discontinue IP if similar unexplained renal and/or electrolyte disturbances subsequently persist or recur during the next cycle of treatment.
Other ≥ Grade 3 non-hematologic treatment-related toxicities	
 • Interrupt IP dosing and provide medical intervention as appropriate • Resume IP at same dose when toxicity resolves to ≤ Grade 2 • If event reoccurs upon re-challenge or at same intensity during next treatment cycle, IP dose may be reduced to 200 mg once a day • If event reoccurs at same intensity once IP dose is reduced to 200 mg once a day, follow the steps above and modify the treatment schedule at a dose of 200 mg once a day.
≥ Grade 2 hematologic or non-hematologic AEs putting a subject at unacceptable risk in the investigator’s opinion	
 • Interrupt IP dosing and provide medical intervention as appropriate • Resume IP at same dose when toxicity resolves to ≤ Grade 1

Table 2: Guidelines for Dose Modifications

NCI CTCAE Toxicity Grade	Action
(related or unrelated to IP)	
 • If event reoccurs upon re-challenge or at same intensity during next treatment cycle, IP dose may be reduced to 200 mg once a day • If event reoccurs at same intensity once IP dose is reduced to 200 mg, follow the steps above and consider modifying the treatment schedule at a dose of 200 mg once a day.

Key: AE=Adverse Event; ANC=Absolute Neutrophil Count; D=Day; G=Grade; IP=Investigational Product; NCI=National Cancer Institute; CTCAE=Common Terminology Criteria for Adverse Events.

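### Protocol Section 8.2.5: as written, the hematologic recovery formula reduces to Day 1 ≥ previous nadir, so the 0.5 has no effect and no regain of counts is required

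*Protocol*

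**What the plan says.** Protocol Section 8.2.5 covers subjects whose ANC or platelets drop to Grade 4, or fall by 50% within Grade 4. For them, "hematologic recovery is required before starting the next cycle at Day 28". Recovery is then defined by an inequality. The left side is the ANC or platelet count on Day 1. The right side is "ANC or platelets nadir from previous Cycle + (0.5 x [ANC or platelets Day 1", with the previous-cycle nadir subtracted inside the bracket. The Day 1 term has the same wording on both sides and carries no cycle label. Only the nadir is tied to the previous cycle.

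Other provisions depend on this definition:

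- Section 8.2.5, after a dose adjustment: "If dose was held, the start of next cycle is based on ANC or platelet recovery, see flow chart in" the same section.
- Section 8.2.4 and Table 2, for Grade 4 neutropenia: "If dose was held, the start of next cycle is based on ANC recovery, see flow chart in" Section 8.2.5.
- Table 2, febrile neutropenia row: "Resume IP at next lower dose level (see dosing table above) after the fever has resolved and ANC recovery". No count is given.
- Section 8.2.5, for late events: "When this occurs later than Cycle 6, contact the Celgene Medical Monitor to discuss if the re-treatment criteria are met".

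The flow chart is Figure 2, Decision Tree for Hematologic Recovery. Its content was not available in the text reviewed.

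**The concern.** A multiplier of 0.5 makes sense only if part of the lost count must be regained. With the same Day 1 value on both sides it cancels, and the only remaining condition is that the count is not below its previous low point. A site following the text literally could restart a subject whose count has not risen at all.

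This is a safety rule. The amendment summary that introduced it gives enhanced hematotoxicity monitoring as the reason. Section 1.4.1 reports an imbalance in deaths, with infection the leading cause among subjects on oral azacitidine.

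No other visible provision sets a mandatory restart count:

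- The Table 2 row for "hematologic or non-hematologic AEs putting a subject at unacceptable risk" depends on the investigator's judgement. Its text in Section 8.2.4 says a subject "may have IP dosing temporarily interrupted until the adverse event returns to" Grade 1 or lower.
- The Section 9.1 platelet trigger (below 25 × 10⁹/L) is advisory.
- The Grade 4 ANC caps in Section 8.2.4 limit the days dosed and say nothing about the count needed to restart.

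**Working it through.** **Symbols.** D is Day 1 of the cycle about to start. N is the nadir of the previous cycle. P is Day 1 of the previous cycle. R is the intended reference count, which the documents do not state. The multiplier 0.5 and the form of the inequality come from Section 8.2.5.

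**The rule as written.** Both Day 1 terms are D:

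D ≥ N + 0.5(D − N) ⇔ 0.5(D − N) ≥ 0 ⇔ D ≥ N.

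For a general multiplier c the condition is (1 − c)(D − N) ≥ 0, so any c below 1 gives the same rule. A numerical check on 200,000 random pairs of D and N found no case where the written rule and D ≥ N disagreed.

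**The rule with a labelled reference.** D ≥ N + 0.5(R − N). The written threshold is N, so it is too low by 0.5(R − N).

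**If R = P.** Let the fall be f = (P − N)/P. The written threshold is (1 − f)P and the labelled one is (1 − f/2)P:

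| Fall f | Written, % of P | Labelled, % of P |
|---|---|---|
| 50% | 50 | 75 |
| 60% | 40 | 70 |
| 80% | 20 | 60 |
| 90% | 10 | 55 |

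**Range over two candidate references.** All counts below are assumed for illustration (× 10⁹/L). For each nadir the first R is a previous-cycle Day 1 and the second a pre-treatment count.

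| Count | N = written threshold | R | N + 0.5(R − N) | Gap |
|---|---|---|---|---|
| ANC | 0.30 | 0.90 | 0.60 | 0.30 |
| ANC | 0.30 | 1.20 | 0.75 | 0.45 |
| ANC, within Grade 4 | 0.20 | 0.40 | 0.30 | 0.10 |
| ANC, within Grade 4 | 0.20 | 0.45 | 0.325 | 0.125 |
| Platelets | 20 | 60 | 40 | 20 |
| Platelets | 20 | 70 | 45 | 25 |

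**Where the readings differ.** If R = P, they differ only when a mid-cycle count puts N below P. Section 6.6.5 schedules weekly counts in Cycles 1–2, counts on Days 1 and 15 in Cycles 3–12, and Day 1 only after that. Appendix J requires at least one count before each Extension Phase cycle. With a single count N = P, so N + 0.5(P − N) = P, which equals the written threshold, and the gap is 0. If R were a pre-treatment count, the gap could be non-zero even with one count per cycle.

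Extra counts do arise in the Extension Phase. Appendix J refers dose modifications to Section 8.2.4, which requires weekly hematology for 2 cycles after a dose adjustment.

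**The case against.** The strongest objection is that the operative rule may be in Figure 2. The dose-hold provisions send sites to the flow chart, which could not be seen and may label the cycles correctly. That stands as a limit: the finding applies to the text definition, and a missing figure cannot be held against the plan. If the figure is correct, though, text and figure conflict on a mandatory rule and the text still needs correcting.

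Second, the reference to the previous cycle could loosely be read as covering the whole bracket, which gives the half-regain rule. Many sites would probably read it that way, and it is very likely the intent. But the label is attached only to the nadir, and a pre-treatment count is also a possible reference. A restart threshold should not rest on inference.

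Third, reach is small. Enrollment is closed, the primary analysis is reported, and subjects still dosing have passed 12 months. This stands, and it limits the importance of the point.

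Fourth, for events after Cycle 6 the Medical Monitor is contacted, and Section 8.2.4 lets the investigator interrupt or delay dosing for Grade 4 neutropenia whatever its cause. These are real safeguards. However, the Medical Monitor discussion is about whether these same criteria are met, and the investigator's option sets no restart count.

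**Conclusion.** The concern holds and should be fixed. That the written definition equals Day 1 ≥ previous-cycle nadir is certain as algebra, provided the two identically worded Day 1 terms mean the same value. It does not show that the sponsor intended no regain.

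The size depends on the unstated reference count. If that is the previous cycle's Day 1, the most plausible choice, the written threshold is too low by half of the fall. The effect on actual dosing is uncertain: the number of affected subjects is unknown, Figure 2 may have guided sites correctly, and the exposure that can still be corrected lies mainly with Extension Phase subjects who have extra counts. Starting a cycle with Grade 4 ANC is not itself the error, since the protocol allows it with shortened dosing. Alpha, power and sample size are unaffected.

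**What to change.** Label each Day 1 by cycle in Section 8.2.5. The most plausible form is:

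next-cycle Day 1 ≥ previous-cycle nadir + 0.5 × (previous-cycle Day 1 − previous-cycle nadir).

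The sponsor's clinical team must confirm the reference count and state what applies when no mid-cycle count was taken. Check that Figure 2 and Table 2 agree with the corrected text, including the ANC recovery condition in the febrile neutropenia row. Notify sites with subjects still on oral azacitidine in the Extension Phase.

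The cost is a one-line protocol correction, a consistency check of one figure and one table, and a note to those sites.
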